(Immediate [baseline-week 12] vs. Delayed [baseline-week 12]) to examine between-group differences for hypothesis 2. We will use Spearman's rank correlation analysis to examine the relationship between baseline-to-week 12 changes in DMN functional connectivity and CBF with baseline-to-week 12 changes in ADAS-cog, MOCA, and QOL-AD in the Immediate PBM group to test hypothesis 3. We will use a two sample t-test on the baseline vs. week-12 differences in CG measures (i.e., Caregiver Burden Inventory, Positive Aspects of Caregiving Scale, Geriatric Depression Scale) to examine between-group differences to test hypothesis 5. We will also evaluate the magnitude of treatment effects on the PP and CG psychometric measures using Cohen d effect sizes for the within-group difference in the Delayed PBM group (baseline-to-week 12 and week 12-to-week 24).

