Dementia is tremendously costly physically, emotionally, and financially. Affected individuals experience a progressive decline in cognition and physical function that leads to a loss of ability to perform basic daily activities such as dressing, eating, and using the toilet. These functional changes are often associated with emotional strain in caregivers and feelings of stress and burden. In many cases, family caregivers are unable to provide care as the disease progresses, and affected individuals are transitioned to long-term care facilities. In fact, the main component of dementia costs is institutional and home-based long-term care rather than medical services. In the U.S. alone, the cost of caring for individuals with dementia were estimated to be \$159 billion to \$215 billion in 2010, with a projected increase to \$379-\$511 billion in 2040 (Hurd et al., 2013). Although home care and long-term care are the largest direct costs of dementia, family caregivers also provide millions of hours of care each year and this is only expected to increase in the coming years. Therefore, an effective treatment for dementia and AD would not only improve memory, cognition and quality of life, but would also have enormous social and economic impact.

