**X. Study Population and Sample Size:**

We will study 10 dyads/pairs of individuals with dementia and their caregivers for this pilot, proof-of-concept study. Five individuals with dementia will be randomized to start PBM treatment with the Vielight Neuro device immediately after baseline assessments (Immediate PBM). Five individuals with dementia will be randomized to the Delayed PBM group, which will not start PBM treatment with the Vielight Neuro device until after completing Week 12 assessments. The sample size was chosen because this is what can be supported with the REAC and Department of Radiology Seed Grant funds. Also, because the Saltmarche et al. (2017) pilot study suggested that cognitive gains achieved by the dementia patients cannot be maintained once PBM treatments are discontinued, we plan to offer the Vielight Neuro devices to primary study participants upon completion of all study procedures so that

they may continue to use. Thus the sample size is also limited by the cost of the Vielight Neuro device (\$875 for research).

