- Geriatric Depression Scale (GDS) short form assesses depressive symptoms in caregivers based on self-report. The GDS short form is a 15-item yes/no scale that is valid in people with and without dementia

Follow-Up Psychometric Assessments (PPs and CGs separately). Follow-up assessments will be performed at weeks 6,12, 18, and 24 for all PPs and CGs. The procedures and measures will be identical to those at baseline.

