**XV. Randomization:** Dyads of PP and CGs be randomized into one of two groups. The Immediate PBM Group will begin treatment with the Vielight Neuro device upon completion of baseline assessments. Treatment will continue for at least 12 weeks. *Because results from Saltmarche et al. pilot study suggest that cognitive gains achieved by patients with dementia may not be maintained without continued PBM treatment, PPs/CGs randomized to the Immediate PBM group will have the option of continuing PBM treatment after completion of Week 12 assessments.* The Delayed PBM Group will not begin treatment with the Vielight Neuro device until after completion of week 12 assessments.

**XVI. Caregiver Device Training** -- Prior to starting the PBM treatments, the CG will be trained how to position the Vielight Neuro device on the PP, how to control, how to clean, and how to maintain the Vielight Neuro device in a single 30 minute session. This training session will either take place at the SF VAMC or at the location of the PP/CG's choice (e.g., their home).

**XVII. Treatment Diary/Log:** To encourage adherence to the home-treatment PBM regimen, CGs will be instructed to log each treatment in the "Daily Home Treatment Journal." CGs will also be instructed to

note changes in the participants' memory, other cognitive processes, and general health conditions in the journal, which will be reviewed at bi-monthly "check-in" calls with the research staff.

**XVIII. Confirmation of Correct Device Use** -- After the first week of treatment, a research staff member will confirm that the CG knows how to properly use and maintain the Vieelight Neuro device. During the "confirmation" appointment, the CG will be asked to demonstrate his/her understanding and ability to correctly place the device on the PP. Any errors will be noted by the study staff and the caregiver will be re-trained or corrected as necessary. The research study staff will also review the treatment diary with the CG to check treatment compliance and its recording. The CG and PP will be encouraged to ask any questions or provide comments on device use which will be noted by study staff.

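### The Protocol Summary sizes treatment effects by before-after Cohen d in the Delayed arm, where one interval is untreated and the other mixes PBM with drift, while the randomised week-12 comparison gets no effect size

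*Combined protocol and SAP*

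**What the plan says.** The Protocol Summary, under Statistical Methodology, closes with: "We will also evaluate the magnitude of treatment effects on the PP and CG psychometric measures using Cohen d effect sizes". It specifies these as "Cohen d effect sizes for the within-group difference in the Delayed PBM group (baseline-to-week 12 and week 12-to-week 24". This is the only effect-size statement in the documents. The Statistical Analysis Plan does not mention Cohen d.

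The design facts that bear on it are:

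- Protocol section XV: "The Delayed PBM Group will not begin treatment with the Vielight Neuro device until after completion of week 12 assessments".
- The same section, on patients and caregivers in the other arm: those "randomized to the Immediate PBM group will have the option of continuing PBM treatment after completion of Week 12 assessments".
- Background section I: "Affected individuals experience a progressive decline in cognition and physical function".
- Section XIV, on the follow-up psychometric assessments at weeks 6, 12, 18 and 24: "The procedures and measures will be identical to those at baseline".
- Section X: "Five individuals with dementia will be randomized to the Delayed PBM group", with five in the Immediate arm. On the choice of 10 dyads: "The sample size was chosen because this is what can be supported with the REAC and Department of Radiology Seed Grant funds".

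The randomised comparison of baseline-to-week-12 change appears as two-sample t-tests: for the cognitive measures in both Summary and SAP, and for three caregiver scales (Caregiver Burden Inventory, Positive Aspects of Caregiving, Geriatric Depression Scale) in the Summary. The SAP adds a repeated-measures ANOVA for ADAS-cog and NPI. None of these carries an effect size or confidence interval.

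**The concern.** The sentence attaches the label of treatment effect to two before-after changes in one arm. During the first interval nobody in that arm is treated. During the second they are treated, but there is no untreated group alongside, because the Immediate arm has already had 12 weeks of PBM and may carry on. No contrast between the two intervals is written.

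The comparison that does remove shared disease course and shared testing, Immediate versus Delayed to week 12, gets no estimate of size. The sample was set by funding and the study is described as a pilot and proof of concept, so estimates and their uncertainty are a large part of what it can deliver. Taken as written, the reported effect size can be non-zero when PBM does nothing, or zero when PBM works.

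The gap is widest for quality of life. It is a stated study aim, but QOL-AD has no between-group test in the Summary or the SAP. It enters only the planned Spearman correlations with imaging within the Immediate arm. The Delayed-arm d values are therefore its only planned measure of treatment effect.

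**Working it through.** **No figure to reproduce.** The documents give no effect size, SD, alpha or power. What follows sets out what each d estimates and then illustrates it on assumed inputs.

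**What each quantity targets.** Work in units of the SD of 12-week change, signed so that positive means improvement. Let τ be the PBM effect, and δ1 and δ2 the drift (disease course plus any retest effect) in weeks 0-12 and 12-24.

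- Delayed arm, baseline to week 12: δ1. No PBM term, whatever τ is.
- Delayed arm, week 12 to week 24: τ + δ2. Equals τ only if δ2 = 0.
- Immediate minus Delayed, baseline to week 12: (τ + δ1) - δ1 = τ.
- Delayed-arm period contrast, (week 24 - week 12) - (week 12 - baseline): τ + δ2 - δ1. Equals τ only if δ1 = δ2.

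**Numbers put in.** All τ and δ values are assumptions. A simulation of 200,000 trials with 5 per arm and bias-corrected d gave the same values as the algebra:

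| τ | δ1 | δ2 | Planned d, 0-12 | Planned d, 12-24 | Between-group d | Period contrast |
|---|---|---|---|---|---|---|
| 0 | +0.3 | +0.3 | 0.30 | 0.30 | 0.00 | 0.00 |
| 0.5 | -0.5 | -0.5 | -0.50 | 0.00 | 0.50 | 0.50 |
| 0.5 | +0.3 | +0.3 | 0.30 | 0.80 | 0.50 | 0.50 |
| 0.5 | +0.5 | +0.1 | 0.50 | 0.60 | 0.50 | 0.10 |

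In scale points, with an assumed SD of 4 for 12-week ADAS-cog change, the second row is a 2-point benefit against a 2-point decline: (2 - 2)/4 = 0 for weeks 12-24 and -2/4 = -0.5 for baseline to week 12, while the true effect is 2/4 = 0.5.

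**Precision with n = 5 in one arm**, if d is standardised by the change SD (the Summary names no standardiser):

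- Small-sample factor J = Γ(m/2) / [√(m/2) Γ((m-1)/2)]. At m = 4 df, J = 0.798, so uncorrected d overstates by 1/0.798 = 1.25, about 25% on average.
- An observed d of 0.5 gives t = 0.5 × √5 = 1.118. Inverting the noncentral t on 4 df gives a 95% CI of -0.46 to 1.41. An observed 0.8 gives -0.26 to 1.79.

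**Precision of the randomised contrast**, 5 versus 5: an observed d of 0.8 gives t = 0.8 × √(5/2) = 1.265 on 8 df, with a 95% CI of -0.52 to 2.08. Here J = 0.903.

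**Choice of standardiser.** Change-SD d divided by raw-SD d is 1/√(2(1 - r)), which is 1.00, 1.29 or 2.24 for an assumed test-retest correlation r of 0.5, 0.7 or 0.9. An unnamed standardiser can therefore more than double the reported value.

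**The case against.** The strongest defence is that the two values are meant to be read together, as each Delayed patient's untreated and treated periods side by side. In the first three rows of the table their gap is exactly the PBM effect. That is a fair reading of the intent. But no subtraction, paired estimate or interval is written, and two sample d values each divided by its own SD do not give one. The gap also works only under equal drift: in the fourth row the period contrast is 0.10 when the effect is 0.50.

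Second, the sentence is supplementary; it says also. This stands. A reader might infer that the tests of hypotheses 1 and 5 are compromised. They are not: they rest on randomised t-tests of week-12 change, and the ANOVA is likewise between groups. For the scales already tested, the between-group d is t × √(2/5), so the remedy there is an addition to reporting.

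Third, retest practice is an inference. The documents say only that identical measures are repeated; they do not discuss practice. It fits the cognitive tests best and is a poor fit for rating scales such as the caregiver inventories and QOL-AD. The point does not depend on it, because the decline that the protocol describes is enough to bias the week 12-24 value for cognition.

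Fourth, the randomised contrast is no more precise: at an observed 0.8 its interval is wider than the within-arm one. True, so the case for it rests on what it estimates. A wait-list comparison also leaves expectation effects in place.

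**Conclusion.** The point holds as a defect in effect-size reporting, confined to one sentence of the Protocol Summary. The baseline-to-week-12 d carries no information on the PBM effect by itself. The week 12-24 d is the PBM effect plus a drift of unknown size and sign. The first conclusion follows from the design alone. The second needs only that drift is not zero, which the protocol's own account of decline makes likely for cognition. The sizes shown rest on assumed drift, effect and SD, and the precision figures on a change-SD standardiser.

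Three stronger readings are not supported:

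- That the week 12-24 value says nothing about PBM. It is confounded, not empty.
- That correct effect sizes would look less favourable. In the second row the between-group d is 0.50 against planned values of -0.50 and 0.00; in the first it is 0.00 against 0.30 and 0.30. The direction depends on drift.
- That the plan repeats the weakness of an uncontrolled earlier study, or supplies the figure for sizing a later trial. Section VII reports improvement in 5 patients without describing that study's design, and neither it nor section X mentions a later trial.

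**What to change.** Replace the sentence in the Summary and put the same text in the SAP, which now has none:

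1. For every PP and CG psychometric measure, including QOL-AD, the treatment-effect size is the Immediate-minus-Delayed difference in baseline-to-week-12 change. Report it in scale points and as a small-sample-corrected standardised difference with the standardiser named, each with a 95% CI. State the direction of benefit for each scale, since higher is worse on ADAS-cog and better on QOL-AD.
2. Label the two Delayed-arm within-group d values descriptive, not treatment effects.
3. If an own-control estimate is wanted, report the paired contrast (week 24 minus week 12) minus (week 12 minus baseline) in the Delayed arm with a 95% CI, as supportive and non-randomised. State that it assumes equal drift, from decline and practice, in both periods.

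The cost is wording and a few lines of analysis; the assessments are already scheduled. The price is candour about precision: intervals at 5 versus 5 will be wide, and point estimates may move either way from what the present sentence would have produced.

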## BACKGROUND

### I. Dementia and Alzheimer's Disease

Dementia is a global health problem of epidemic proportion with no present cure. It is estimated to affect 5.4 million people in the United States (Alzheimer's World Report, 2016) and 46.8 million people worldwide (World Alzheimer Report, 2016). This represents 1 in 9 individuals aged 65 years or older and 1 in 3 aged 85 or older (Alzheimer's World Report, 2016). Over the next 40 years, it is expected that longer life expectancies coupled with demographic trends will result in a dramatic increase in dementia prevalence, with 16 million cases in the U.S. and 131.5 million worldwide. Alzheimer's disease (AD), the most common cause of dementia in the elderly (Blennow et al., 2006), exerts a deleterious effect on patients, caregivers, and families (Reitz et al., 2011).

Though a few Federal Food and Drug Administration (FDA)-approved pharmacotherapies do exist for the treatment of AD, these produce symptomatic improvements but are not curative nor have been demonstrated to slow the progression of the disease. Thus family members of AD patients are faced with the eventual decision of becoming at-home caregivers or relying on long-term care facilities. Home care assistance can help to lengthen the time AD patients are able to remain living in the community, yet a significant number of patients eventually require long-term care facilities. Severe declines in cognition also result in increased accidents and emergency department visits, often resulting in long-term hospitalization.

Dementia is tremendously costly physically, emotionally, and financially. Affected individuals experience a progressive decline in cognition and physical function that leads to a loss of ability to perform basic daily activities such as dressing, eating, and using the toilet. These functional changes are often associated with emotional strain in caregivers and feelings of stress and burden. In many cases, family caregivers are unable to provide care as the disease progresses, and affected individuals are transitioned to long-term care facilities. In fact, the main component of dementia costs is institutional and home-based long-term care rather than medical services. In the U.S. alone, the cost of caring for individuals with dementia were estimated to be \$159 billion to \$215 billion in 2010, with a projected increase to \$379-\$511 billion in 2040 (Hurd et al., 2013). Although home care and long-term care are the largest direct costs of dementia, family caregivers also provide millions of hours of care each year and this is only expected to increase in the coming years. Therefore, an effective treatment for dementia and AD would not only improve memory, cognition and quality of life, but would also have enormous social and economic impact.

### II. Currently Available Dementia Treatments

All legally marketed treatments for AD are pharmacological. There are currently 3 pharmacological ligands available with FDA-approved indications for use as treatments of moderate to severe dementia of the Alzheimer's type: donepezil (23mg QD, PO), rivastigmine (13.3mg QD, transdermal patch), and memantine (10 mg BID or 28mg/day QD extended release, PO). Additionally, a combination of donepezil and memantine is available as a single capsule formulation named Namzaric.

Two of these ligands, donepezil and rivastigmine, have their mechanisms of action through non-competitive inhibition of cholinesterases, the enzymes responsible for the hydrolysis of choline esters (Deardorff, Feen et al. 2015). Donepezil is a reversible inhibitor of acetylcholinesterase, the enzyme predominantly responsible for the breakdown of the neurotransmitter acetylcholine, while rivastigmine is a pseudo-irreversible inhibitor of acetylcholinesterase and butylcholinesterase, which plays a minimal role centrally compared to acetylcholinesterase. The neurotransmitter acetylcholine is well-established to play a critical role in learning and memory (Hasselmo 2006). Several deficits in the cholinergic system

have been identified in post-mortem brain examinations of AD (Ferreira-Vieira, Guimaraes et al. 2016), and these ligands are capable of reducing the cognitive and functional deficits experienced by moderate to severe AD patients (Farlow, Salloway et al. 2010; Farlow, Grossberg et al. 2013).

The third ligand, memantine, has its mechanism of action through the anti-competitive antagonism of glutamatergic N-methyl-D-aspartate (NMDA) receptors (Chen and Lipton 1997) across the brain as well as having neuroprotective effects (Hardingham and Bading 2010). Memantine has also been demonstrated to reduce cognitive and functional deficits experienced by moderate to severe AD patients, even when already receiving donepezil (Reisberg, Doody et al. 2003; Tariot, Farlow et al. 2004; Grossberg, Manes et al. 2013).

All of these ligands have their primary mechanisms of action through influences on neurotransmitter systems with evidence of disruption in AD; however, evidence also exists suggesting these ligands affect the mitochondrial dysfunction observed in AD as well. Repeated doses of donepezil or memantine reduce neurotoxic effects and memory impairments caused by okadaic acid (Kamat, Tota et al. 2011) while repeated doses of rivastigamine reduces the biochemical alterations and memory impairments caused by 3-nitropropionic acid in rats (Kumar and Kumar 2009). These pharmacotherapies were demonstrated to protect against those memory impairments due to their ability to preserve mitochondrial function. Thus interest in the mitochondrial cascade hypothesis of AD has been growing, along with evidence of amyloid beta and tau being tied to mitochondrial dysfunction (Spuch, Ortolano et al. 2012; Swerdlow, Burns et al. 2014; Benek, Aitken et al. 2015).

### **III. Limitations of Currently Available Dementia Treatments**

Though several compounds are under clinical investigation for delaying or preventing the progression from the stage of mild cognitive impairment to AD, there have been no successful trials for over 15 years. All FDA-approved therapies for the treatment of AD produce symptomatic improvement only. Though the pharmacotherapies described above are highly valuable in this patient population, there remains a significant need for treatments for long term symptomatic improvement and disease-modifying potential, particularly therapies that can be used in combination with current pharmacotherapeutic options.

Finally, the number of patients experiencing adverse events is considerable, particularly with the cholinesterase inhibitors. In the pivotal trial of 23mg/day donepezil for moderate to severe AD, 74% of patients experienced at least one adverse reaction to the medication with 19% of patients discontinuing the medication for this reason (Farlow, Salloway et al. 2010). The most common adverse reactions included nausea (12%), vomiting (9%), diarrhea (8%), anorexia (5%), and dizziness (5%). In the pivotal trial of 13.3mg/day rivastigmine for severe AD, 75% of patients experienced at least one adverse reaction to the medication with 26% of patients discontinuing the medication for this reason (Farlow, Grossberg et al. 2013). The most common adverse reactions included erythema at application site (13%), agitation (12%), urinary tract infection (8%), dermatitis at application site (8%), and falls (8%). Thus there exists a large proportion of the moderate to severe AD population for whom acetylcholinesterase inhibitors are not an option, as can be seen in the high discontinuation rates (19% and 26%) due to side effects in the two clinical trials.

### **IV. Vielight Neuro Device**

Vielight Inc. has developed a novel photobiomodulation device, the Vielight Neuro. The devices are not labeled for treating dementia or AD and would be described as non-regulated, "low risk general wellness

products,” according to the Food and Drug Administration (FDA) document, “General Wellness: Policy for Low Risk Devices”, released on July 29, 2016.

Vielight Neuro delivers painless, non-invasive, non-thermal, non-laser, pulsed (40 Hz; 50% duty cycle), near-infrared light (810 nm wavelength) through 5 non-laser light emitting diodes (LEDs) over a 20 minute treatment session. The device is intended for daily use at home and is powered by rechargeable NiMH batteries. One of the Vielight Neuro’s LEDs is placed inside the nose for intranasal transmission of light energy and the remainder four LEDs are positioned over the skull for transcranial transmission. The transcranial LEDs are held in position by two lateral stainless steel bands (see Figure 1).

**Figure 1.** Vielight Neuro device

